7.2.2. Toxicology Studies

Repeat-dose toxicology studies of 1- and 3-month treatment duration have been conducted with ACE 536 in Sprague-Dawley rats and cynomolgus monkeys to evaluate the toxicity of ACE-536. Recovery periods of up to 10 weeks were included as part of these studies. Findings from toxicology studies, described in more detail in the Investigator's Brochure, were different between rats and monkeys, though the expected pharmacologic effects of the drug were observed in both species.

ACE-536 exhibited favorable and predictable pharmacokinetic properties in both species. Serum concentrations of ACE-536 followed first-order absorption and first-order elimination kinetics after the first dose. The PK profiles of ACE-536 were similar among males and females, independent of dose level, and achieved peak or near peak mean serum concentrations at approximately 4 days in rats and 2 to 3 days in monkeys. The C_{max} and AUC were linear and approximately proportional to dose up to the highest dose levels evaluated. The serum terminal elimination half-life in rat is approximately 5 days and in monkey is 6 to 7 days, and clearance is independent of dose level and route of administration (SC vs IV).

Key findings identified in the 1- and 3-month rat toxicology studies included decreased heart, lung and prostate weight with no histopathology correlate, adrenal gland necrosis/congestion, and minimal liver necrosis. Stomach mineralization was only observed in the 1-month rat study.

Membranoproliferative glomerulonephritis was observed in rat and monkey studies, as well as increased BUN and creatinine. At the highest dose (30 mg/kg) in the monkey study, glomerulonephritis was accompanied by fibrosis and hemorrhage of the interstitium. The findings were suggestive of immune complex deposition, which could be associated with anti-drug antibodies; however, a direct effect of the drug cannot be excluded.

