7.4. Potential Risks of Human Use

Increases in hematologic parameters (RBC, hemoglobin, hematocrit, reticulocytes) are expected pharmacologic effects of ACE-536 treatment. Increases in systolic and diastolic blood pressures may occur in concert with increases in hemoglobin values. Excessive or rapid increases in hemoglobin or blood pressure may occur and will be monitored. Dose modifications rules for individual subjects and dose escalation/reduction rules will be utilized to minimize risks associated with increased RBC parameters.

Adverse events observed in the Phase 1 study in healthy volunteers that were considered probably or possibly related to study drug included injection site hemorrhage, injection site macule, dry skin, hyperesthesia, muscle spasms, myalgia, generalized pruritis, and papular rash.

Membranoproliferative glomerulonephritis was observed in both rats and monkeys, likely secondary to immune complex deposition. These findings were associated with increases in serum BUN and creatinine. The presence of immune complexes in renal tissue from monkeys treated with ACE-536 was demonstrated by immunohistochemistry.

The growth of heart and lungs was slightly reduced in rats exposed to ACE-536 as compared with control animals; these decreased heart and lung weights were reversible and there was no

corresponding histology finding. These findings were not replicated in the monkey toxicology studies; the potential for these adverse effects in humans is unknown.

Based on rat toxicology studies, treatment with ACE-536 may affect the adrenal gland. These findings were specific to the rat as they were not replicated in the monkey toxicology studies.

As with all biologics, there is the potential for anti-drug antibodies that can be associated with increased drug clearance and hypersensitivity reactions. Anti-drug antibody formation against ACE-536 as well as human ActRIIB protein will be monitored in the initial clinical studies.

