15.2.5. Anti-drug antibody analysis

The results of anti-drug and neutralizing antibody testing for ACE-536 and human ActRIIB protein versus time will be presented. Exploratory analysis will be performed on the potential effect of anti-drug antibodies on ACE-536 PK and drug exposure if anti-drug antibody tests are deemed positive.

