15.5. Deviation from Original Analysis Plan

A formal Statistical Analysis Plan (SAP) for the analysis and presentation of data from this study will be prepared before the database lock. Deviations from the statistical analyses outlined in this protocol will be indicated in this plan; any further modifications will be noted in the final clinical study report.

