5.8. Safety Analysis

The safety endpoints will be summarized by dose cohort using the Safety Population. The safety endpoints include the incidence of dose-limiting toxicities (DLTs), treatment emergent adverse events, changes in laboratory tests, vital signs and ECG's.

Adverse events will be coded using MedDRA Version 15.1 and above. Severity of AEs will be coded using National Cancer Institute Common Toxicity Criteria for Adverse Events version 4.0 (NCI-CTCAE v4.0).

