5.8.3. Laboratory Evaluations

Results from the following laboratory parameters, recorded at their respective time points will be summarised by dose cohort and time point:

Haematology: (Screening, Days 1, 8 and 15 of each cycle, End of Treatment, Post Treatment Follow Up and End of Study).

RBC, WBC with differential, hemoglobin, hematocrit, haptoglobin (optional), reticulocyte count, platelet count, MCV, MCH, MCHC, RDW, and nRBCs

Chemistry: (Screening, Days 1 and 15 of Cycle 1, and Days 1 of each subsequent cycle, End of Treatment and End of Study).

Sodium, potassium, chloride, carbon dioxide/bicarbonate (optional), AST, ALT, lactate dehydrogenase (LDH), total bilirubin, indirect bilirubin, alkaline phosphatase, blood urea nitrogen (BUN)/urea, creatinine, GGT, calcium, phosphorus, glucose, amylase, lipase, total protein, albumin, and uric acid

Urine: (Day 1 of Cycles 1, 2 and 4, End of Treatment and End of Study).

PH, specific gravity, protein, glucose, ketones, blood, leukocyte esterase, and nitrite, with microscopic examination if indicated; Microalbumin and creatinine

Urine Chemistry: (Day 1 of Cycles 1, 2 and 4, End of Treatment and End of Study).

Microalbumin and creatinine will be performed by the central lab.

Categorical and numeric variables will be presented separately.

Actual values and changes in haematology and biochemistry laboratory values from baseline will be summarised by dose cohort and by time point.

Shift tables for the haematology and biochemistry laboratory parameters comparing values above, within and below the normal reference range at baseline to the end of treatment visit will be presented using standard reference ranges.

Actual urine laboratory values will be summarised by dose cohort.

Peripheral blood smears are taken at Screening, Day 1 of Cycles 1, 2, and 5 and at the end of treatment visit. These data will be listed only.

All laboratory values will be listed for all patients.

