5.13. Changes in Conduct or Planned Analyses from the Protocol

Major changes between SAP and the planned analysis in Protocol Amendment 4 are described below:

Changes	Rationale
Definition of baseline hemoglobin	Protocol definition: Baseline hemoglobin will be the average of at least two measures (not influenced by transfusion within 7 days of measurement); one measure performed within one day prior to Cycle 1 Day 1 and the other performed 7-28 days prior to Cycle 1 Day 1. This definition is revised in this SAP to reflect the derivation rule implemented for this study.
Remove Efficacy Evaluable (EE) population	EE population is very similar to ITT population. ITT provides more conservative estimate of treatment effect.

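### The SAP omits, without declaring it, both anti-drug antibody analyses planned in the protocol, and its tables count patient-level renal worsening only for serum markers at one visit

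*SAP*

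**What the plan says.** **Why antibodies and kidneys matter here.** Protocol 7.2.2 and 7.4 report membranoproliferative glomerulonephritis in rats and monkeys, with raised BUN and creatinine. Protocol 7.2.2 comments: "The findings were suggestive of immune complex deposition, which could be associated with anti-drug antibodies". The same sentence goes on to say that a direct drug effect is not ruled out. Protocol 7.4 adds that antibodies can raise drug clearance and cause hypersensitivity, and states: "Anti-drug antibody formation against ACE-536 as well as human ActRIIB protein will be monitored in the initial clinical studies".

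**What the protocol plans.** Protocol 15.2.5: "The results of anti-drug and neutralizing antibody testing for ACE-536 and human ActRIIB protein versus time will be presented". It also plans an exploratory analysis of the "potential effect of anti-drug antibodies on ACE-536 PK and drug exposure if anti-drug antibody tests are deemed positive". Protocol 15.2.3 plans summaries over time of change from baseline in clinical laboratory values, with shift tables where appropriate. It makes no exception for urine.

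**What the SAP plans.** SAP 5.8: "The safety endpoints include the incidence of dose-limiting toxicities (DLTs), treatment emergent adverse events, changes in laboratory tests, vital signs and ECG's". ADA does not appear there, in the laboratory section (5.8.3) or in the PK sections (5.9.1 to 5.9.5). It is found only in the reproduced schedule of events and its footnotes. For urine, SAP 5.8.3 says: "Actual urine laboratory values will be summarised by dose cohort". Haematology and biochemistry get actual values, change from baseline by time point, and a shift table from baseline to the end of treatment (EOT) visit.

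**Declaring changes.** Protocol 15.5: "Deviations from the statistical analyses outlined in this protocol will be indicated in this plan". SAP 5.13: "Major changes between SAP and the planned analysis in Protocol Amendment 4 are described below". It then lists two items, the baseline hemoglobin definition and removal of the Efficacy Evaluable population.

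**The concern.** The protocol names a kidney toxicity in two animal species, offers immune complexes as its likely origin, and plans antibody analyses. A SAP that says nothing about antibodies leaves the study report with no planned antibody incidence, no time course by cohort and no comparison of exposure by antibody status.

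The urine plan adds to this. Protocol 9.3.2 excludes proteinuria only from Grade 2 upward, so some patients may enter with a lesser degree. Actual values by cohort and visit cannot then separate new or worsening proteinuria in a patient from proteinuria already present. The AE tables may not catch it either: under protocol 14.1 an abnormal laboratory result is not reported as an AE unless it comes with signs or symptoms, leads to discontinuation of treatment, or is judged clinically relevant.

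There is also a PK side. SAP 5.9.4 fits a one-compartment model to all concentrations from the first dose to end of study. If antibodies raised clearance in some patients partway through, the plan has no step that would look for it.

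**Working it through.** The plan gives no figure to reproduce on this point, so the check is a comparison of texts with a few counts.

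**1. ADA analyses, protocol against SAP.**

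| Protocol 15.2.5 | SAP analysis sections |
|---|---|
| ADA and neutralizing antibody results over time, for ACE-536 and ActRIIB | none |
| ADA effect on PK and exposure, if positive | none |

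Two are planned and none is carried over. By contrast, the neighbouring protocol 15.2.4 is carried into SAP 5.9 closely, including dose proportionality and exposure-response.

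**2. Declaration.** SAP 5.13 lists 2 changes, of which 0 concern ADA.

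**3. Chemistry visits.** From SAP 5.8.3 and the schedule, post-baseline chemistry falls at C1D15, C2D1, C3D1, C4D1, C5D1, EOT and EOS: 1 + 4 + 2 = 7. The shift table uses EOT only, so 1 of 7. A patient whose creatinine left the normal range during dosing and returned by EOT, or who moved out of range only at EOS, is not counted as shifted.

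**4. Urine visits.** SAP 5.8.3 lists C1D1, C2D1, C4D1, EOT and EOS, so 4 are post-baseline. Within-patient change or shift is stated for 0 of the 4.

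**5. Which exposure measure could show an antibody effect.** The schedule places ADA samples at C1D1, C4D1, EOT and EOS. The row aligns with hemoglobin electrophoresis, whose C1D1, C4D1 and EOT timing SAP 5.7.2.4 gives in words. The first post-baseline ADA sample is therefore at C4D1, Day 64. The first-dose parameters in SAP 5.9.3 use samples up to C2D1, Day 22, which is 64 − 22 = 42 days earlier. Splitting first-cycle Cmax or AUC by a post-baseline ADA result would group patients by something measured six weeks later, and could not show the effect of antibodies that arose after Cycle 1. Concentrations from Cycle 4 onward can. CL/F uses all samples and so mixes earlier and later cycles. It is still worth tabulating, but would dilute a late effect.

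**The case against.** **The kidney risk is analysed.** A reader might infer that the SAP leaves it unexamined. The documents do not support that. Protocol 7.4 ties the animal finding to serum BUN and creatinine. Both are in the SAP chemistry panel, with actual values and change from baseline by cohort and time point, plus the EOT shift. SAP 5.2 includes minimum and maximum in its descriptive statistics, so a large single rise would show at its visit. Renal AEs fall under the tables in SAP 5.8.2. This stands in full. What these summaries lack is a count of patients who worsened at any time.

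**ADA results are not lost.** SAP 5.2 puts all study data in listings, and SAP 1 says the plan is to be read with the protocol. Protocol 15.2.5 specifies no table, and its PK analysis is exploratory and conditional. This stands in part. A listing gives no incidence, time course by cohort or relation to exposure, and where the SAP intends listing only (blood smears, physical examination, several exploratory measures) it says so.

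**Urine has some baseline reference.** A reader might infer that there is none. SAP 5.8.3 opens by summarising laboratory results by cohort and time point, and the urine time points include C1D1, so cohort values can be set against Day 1. SAP 5.8 also names changes in laboratory tests generally. The gap is that no within-patient change or shift is stated for urine.

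**SAP 5.13 covers major changes only.** The sponsor might call this one minor. Protocol 15.5 sets no such threshold.

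**A worst-value shift is not required by the protocol.** That is right: it asks for shift tables as appropriate. This part of the fix is an improvement, not the repair of a breach.

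**Conclusion.** The point holds in this form. Both planned ADA analyses are missing from the SAP and their removal is undeclared. Urine protein, microalbumin and creatinine have no stated within-patient comparison with baseline. Category shifts in serum renal markers are counted at 1 of 7 scheduled post-baseline visits. Renal safety rests on serum BUN and creatinine change by visit, the EOT shift and the AE tables, and no planned table relates it to ADA status.

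This should be corrected, but it does not touch the primary efficacy estimate. It does not show that the study misses a renal signal, nor that antibodies explain the animal finding; the protocol treats that link as possible only.

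I give no count of affected samples. The cohort sizes in SAP 3.1 sum to 6 × 5 + 5 + 30 = 65 against a stated total of 64, and SAP 3.3 lets rollover patients skip the EOS visit.

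The conclusion assumes that protocol 15.2.5 and 15.5 read the same in the amendment the SAP cites (Amendment 4), and that urine chemistry is not meant to fall under biochemistry in SAP 5.8.3. The separate sentence on actual urine values suggests it is not.

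**What to change.** 1. Add an ADA subsection to the SAP. Give the number and percent of patients ADA-positive and neutralizing-positive at baseline and post-baseline, by cohort and visit, for ACE-536 and ActRIIB. If positives occur, summarise concentrations from Cycle 4 onward and CL/F by ADA status; do not split first-cycle Cmax or AUC by post-baseline ADA. If the analysis was removed or is reported elsewhere, say so in SAP 5.13 with the reason.
2. In SAP 5.8.3, add within-patient change from baseline in the urine microalbumin/creatinine ratio and a shift table for dipstick protein. SAP 5.1 already defines the baseline to use.
3. Add a shift from baseline to worst post-baseline value for laboratory parameters, including BUN and creatinine, and keep the EOT shift beside it. The worst of up to seven values will exceed a single baseline in some patients by chance, and there is no control arm, so the two columns should be read together.

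Cost: SAP wording and a few descriptive tables from samples already scheduled, with no new visits or assays. If few patients are ADA-positive, the comparison by ADA status will be little more than a description of individual patients.

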5.8.1. Dose Limiting Toxicities

A Dose-Limiting Toxicity (DLT) is defined as any of the following toxicities, at any dose level occurring within 28 days of the first administered dose:

- Treatment related serious adverse event (SAE) of Grade \geq 3
- Treatment related non-hematologic adverse event (AE) of Grade \geq 3
- Treatment related hematologic AE of Grade \geq 4

Incidence rates of DLTs will be presented by dose cohort. Details of DLTs will be presented in listings.

5.8.2. Adverse Events

All AEs and SAEs occurring after the Cycle 1 Day 1 dose through 56 days after the last study drug administration are to be reported and documented on the AE CRF. All AEs collected in this study are treatment emergent adverse events (TEAE). A drug-related TEAE is defined as any TEAE related to the study medication as assessed by the investigator or with missing assessment of the causal relationship.

The following summaries will be presented by dose cohort and by low/high dose for all dosed patients as well as for NTD and TD patients separately:

- Number and percentage of patients reporting each AE, categorized by System Organ Class (SOC) and Preferred Terms (PT)
- Number and percentage of patients reporting each AE experienced by $\geq 5\%$ of patients in all patients by PT
- Number and percentage of patients reporting SAE, categorized by System Organ Class (SOC) and Preferred Terms (PT)
- Number and percentage of patients reporting Grade ≥ 3 AE, categorized by System Organ Class (SOC) and Preferred Terms (PT)
- Number and percentage of patients reporting related AE, categorized by System Organ Class (SOC) and Preferred Terms (PT)
- Number and percentage of patients reporting AE leading to drug withdrawal, categorized by System Organ Class (SOC) and Preferred Terms (PT)
- Number and percentage of patients reporting each AE categorized by SOC, preferred term, and maximum severity grade group

Note that counting will be by subject, not event, and subjects are only counted once within each SOC or preferred term. If a subject experiences the same AE at more than one severity, or with more than one relationship to study drug, the most severe rating or the stronger causal relationship to study drug will be given precedence. Any missing severity, causality, or outcome will not be imputed and classed as unknown.

All AEs will be listed. The following listings will also be provided: 1) patients with SAEs; 2) patients with Grade ≥ 3 AEs; and 3) patients with AEs leading to discontinuation

5.8.3. Laboratory Evaluations

Results from the following laboratory parameters, recorded at their respective time points will be summarised by dose cohort and time point:

Haematology: (Screening, Days 1, 8 and 15 of each cycle, End of Treatment, Post Treatment Follow Up and End of Study).

RBC, WBC with differential, hemoglobin, hematocrit, haptoglobin (optional), reticulocyte count, platelet count, MCV, MCH, MCHC, RDW, and nRBCs

Chemistry: (Screening, Days 1 and 15 of Cycle 1, and Days 1 of each subsequent cycle, End of Treatment and End of Study).

Sodium, potassium, chloride, carbon dioxide/bicarbonate (optional), AST, ALT, lactate dehydrogenase (LDH), total bilirubin, indirect bilirubin, alkaline phosphatase, blood urea nitrogen (BUN)/urea, creatinine, GGT, calcium, phosphorus, glucose, amylase, lipase, total protein, albumin, and uric acid

Urine: (Day 1 of Cycles 1, 2 and 4, End of Treatment and End of Study).

PH, specific gravity, protein, glucose, ketones, blood, leukocyte esterase, and nitrite, with microscopic examination if indicated; Microalbumin and creatinine

Urine Chemistry: (Day 1 of Cycles 1, 2 and 4, End of Treatment and End of Study).

Microalbumin and creatinine will be performed by the central lab.

Categorical and numeric variables will be presented separately.

Actual values and changes in haematology and biochemistry laboratory values from baseline will be summarised by dose cohort and by time point.

Shift tables for the haematology and biochemistry laboratory parameters comparing values above, within and below the normal reference range at baseline to the end of treatment visit will be presented using standard reference ranges.

Actual urine laboratory values will be summarised by dose cohort.

Peripheral blood smears are taken at Screening, Day 1 of Cycles 1, 2, and 5 and at the end of treatment visit. These data will be listed only.

All laboratory values will be listed for all patients.

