2. For the dose escalation phase of the study: documented diagnosis of β -thalassemia intermedia (transfusion dependent patients must not have begun regular transfusions at age < 4.0 years). For the expansion cohort: documented diagnosis of β -thalassemia (including β -thalassemia major or β -thalassemia intermedia).
3. Prior splenectomy or spleen size < 18 cm in the longest diameter by abdominal ultrasound (dose escalation cohorts only).

4. Anemia, defined as:
 - a. Mean hemoglobin concentration < 10.0 g/dL of 2 measurements (one performed within one day prior to Cycle 1 Day 1 and the other performed during the screening period [Day -28 to Day -1]) in non-transfusion dependent patients, defined as having received < 4 units of RBCs within 8 weeks prior to Cycle 1 Day 1, OR
 - b. Transfusion dependent, defined as requiring \geq 4 units of RBCs every 8 weeks (confirmed over 6 months prior to Cycle 1 Day 1).
5. Aspartate aminotransferase (AST) or alanine aminotransferase (ALT) < 3 x upper limit of normal (ULN).
6. Serum creatinine \leq 1.5 x ULN.
7. Females of child bearing potential (defined as sexually mature women who have not undergone hysterectomy or bilateral oophorectomy, or are not naturally postmenopausal \geq 24 consecutive months) must have negative urine or blood pregnancy test prior to enrollment and use adequate birth control methods (abstinence, oral contraceptives, barrier method with spermicide, or surgical sterilization) during study participation and for 12 weeks following the last dose of ACE-536. Males must agree to use a latex condom during any sexual contact with females of child-bearing potential during study participation and for 12 weeks following the last dose of ACE-536, even if he has undergone a successful vasectomy. Patients must be counseled concerning measures to be used to prevent pregnancy and potential toxicities prior to the first dose of ACE-536.
8. Patients are able to adhere to the study visit schedule, understand and comply with all protocol requirements.
9. Understand and able to provide written informed consent.

Exclusion Criteria:

1. Any clinically significant pulmonary (including pulmonary hypertension), cardiovascular, endocrine, neurologic, hepatic, gastrointestinal, infectious, immunological (including clinically significant allo- or auto-immunization) or genitourinary disease considered by the investigator as not adequately controlled prior to Cycle 1 Day 1.
2. Folate deficiency.

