14. ASSESSMENT OF SAFETY

14.1. Adverse Event Definitions

Adverse Event

An adverse event (AE) is any untoward medical occurrence in a patient or clinical investigation patient administered a study drug, which does not necessarily have a causal relationship with this treatment. An AE can therefore be any unfavorable and unintended sign (including an abnormal laboratory finding), symptom, or disease temporally associated with the use of the study drug whether or not it is considered related to the study drug.

Abnormal laboratory and other abnormal investigational findings (e.g., physical exam, ECG) should not be reported as AEs unless they are associated with clinical signs and symptoms, lead to treatment discontinuation, or are otherwise considered clinically relevant by the investigator. In cases of surgical or diagnostic procedures, the condition/illness leading to such a procedure is considered as the AE rather than the procedure itself. In case of a fatality, the cause of death is considered as the AE, and the death is considered as its outcome.

Unexpected Adverse Events

An unexpected AE is an AE that is not described in nature or severity in the Investigator's Brochure.

Events Not to Be Considered as Adverse Events

Pre-existing medical conditions/signs/symptoms present before the Screening period that do not worsen in severity or frequency during the study are defined as Baseline Medical Conditions, and are not to be considered AEs. Anticipated day-to-day fluctuations of pre-existing conditions, including the disease under study, that do not represent a clinically significant exacerbation or worsening need not be considered adverse events.

Serious Adverse Event

A serious adverse event (SAE) is any AE, occurring at any dose level/regimen and regardless of causality that:

- Results in death.
- Is life-threatening: Life-threatening means that the patient was at immediate risk of death from the reaction as it occurred (i.e., it does not include a reaction which hypothetically might have caused death had it occurred in a more severe form).
- Requires inpatient hospitalization or prolongation of existing hospitalization; however, a hospitalization for an elective procedure will not be considered an SAE.
- Results in persistent or significant disability/incapacity.

- Is a congenital anomaly/birth defect.

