5. STATISTICAL METHODOLOGY

5.1. Definitions

Transfusion Dependent (TD)

Based on protocol, TD patients are defined as those who required ≥ 4 units of RBCs every 8 weeks (confirmed over 6 months prior to Cycle 1 Day 1).

For programming implementation, a patient is defined as TD if the total RBCs is ≥ 11 units during 26 weeks on or prior to Cycle 1 Day 1.

Non-Transfusion dependent (NTD)

NTD patients are those who do not meet the above definition for TD. For programming implementation, NTD patients are defined as those who received < 11 units of RBCs during 26 weeks on or prior to Cycle 1 Day 1.

Baseline Hemoglobin

Baseline hemoglobin will be an average of hemoglobin measurements within 28 days of Cycle 1 Day 1, excluding measurements within 14 days following RBC transfusion.

Baseline Transfusion Burden

Baseline transfusion burden will be calculated as the total amount of RBC transfusions during the 12 weeks on or prior to Cycle 1 day 1.

Baseline for Other Parameters

Baseline erythropoietin (EPO) is defined as the maximum test value within 28 days of Cycle 1 Day 1. For all other parameters, baseline is defined as the last observation on or prior to Cycle 1 Day 1.

Transfusion Unit Conversion

The transfusion amount measured in unit “mL” will be converted to “units” according to medical review.

End of Treatment (EOT)

Procedures and evaluations for the end of treatment visit should be performed 28 days (± 7 days) after the last dose of ACE-536.

End of Study (EOS)

Procedures and evaluations for the end of study visit should be performed 28 days (± 7 days) after the Day 113/EOT visit (56 days after the last dose of ACE-536).

Combined Dose Groups

Low dose group includes patients on 0.2mg/kg and 0.4 mg/kg dose cohorts. High dose group include patients with dose level 0.6 mg/kg and above. Suitable summaries may be presented by low/high dose as specified.

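### Laboratory shift tables cannot show worsening in patients already above the normal range at baseline, and no other planned laboratory table counts those patients

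*SAP*

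**What the plan says.** SAP 5.8.3 plans "Shift tables for the haematology and biochemistry laboratory parameters comparing values above, within and below the normal reference range at baseline" with those at end of treatment, judged against what it calls standard ranges. That gives three categories and two time points. For chemistry and for haematology other than haemoglobin, SAP 5.1 sets the starting point: "For all other parameters, baseline is defined as the last observation on or prior to Cycle 1 Day 1".

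Protocol 9.3.1, criteria 5 and 6, sets the entry limits: AST or ALT strictly below 3 x ULN, and serum creatinine at or below 1.5 x ULN. Both limits lie above the top of the normal range.

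Protocol 7.4 describes membranoproliferative glomerulonephritis in rats and monkeys and adds: "These findings were associated with increases in serum BUN and creatinine".

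SAP 5.8 applies NCI-CTCAE v4.0 to the severity of adverse events. Neither document plans to grade laboratory values as such. On when an abnormal laboratory finding becomes an adverse event, Protocol 14.1 says that such findings "should not be reported as AEs unless they are associated with clinical signs and symptoms", lead to stopping treatment, or are thought clinically relevant by the investigator. Protocol 14.5 adds that clinically relevant laboratory changes must be recorded as adverse events.

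SAP 5.8.3 also summarises actual values and changes from baseline by cohort and time point, and lists all values.

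**The concern.** A shift table is the usual place where a reader finds how many patients got worse on a laboratory test. Here its scale stops at the ULN. The plan lets patients in above the ULN for creatinine and transaminases, and for them the table has no cell in which worsening can be recorded. A patient who moves slightly across the limit is counted, and a patient whose raised value multiplies is not.

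This matters most for creatinine. It is the marker that the protocol links to its renal finding in animals, and Protocol 7.2.2 says that a direct effect of the drug could not be excluded. The hepatic case is weaker: 7.2.2 reports only minimal liver necrosis in rats, and 7.4 does not list liver injury as a potential human risk. AST and ALT belong here mainly because the entry limit expressly allows a raised start.

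At stake is whether the study report holds a per-patient count of worsening on these tests.

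**Working it through.** The plan gives no figure to reproduce on this point. The check applies the SAP's own rule to values within the entry limits, then goes through the other planned outputs.

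**Step 1. The rule.** Let x = value / ULN. The category is above if x > 1, below if x is under the lower limit, and within otherwise. If baseline b > 1 and the end of treatment value e ≥ b, then e > 1. The cell is therefore above to above whatever the ratio e/b.

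**Step 2. Examples.** Baselines respect the entry limits (creatinine ≤ 1.5, ALT < 3). The end values are assumed, for illustration only.

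| Test | Baseline (x ULN) | End of treatment (x ULN) | Ratio | Cell | Counted as a shift? |
|---|---|---|---|---|---|
| Creatinine | 1.2 | 2.4 | 2.4/1.2 = 2.0 | above to above | No |
| Creatinine | 1.5 | 4.5 | 4.5/1.5 = 3.0 | above to above | No |
| ALT | 2.0 | 8.0 | 8.0/2.0 = 4.0 | above to above | No |
| ALT | 2.9 | 15 | 15/2.9 = 5.17 | above to above | No |
| ALT | 0.9 | 1.05 | 1.05/0.9 = 1.17 | within to above | Yes |

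The smallest relative change is the only one that counts. A similar loss occurs inside the range: creatinine from 0.45 to 0.95 x ULN is a ratio of 0.95/0.45 = 2.11 and stays within to within, assuming the lower limit is no higher than 0.45 x ULN.

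**Step 3. Do other outputs supply the count?**

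| Planned output | Shows a large rise? | Counts patients whose abnormal value worsened? |
|---|---|---|
| Shift table (SAP 5.8.3) | Not from an above-range start | No |
| Values and changes by cohort and visit (SAP 5.2, 5.8.3) | Yes, in the maximum | No |
| Listings (SAP 5.8.3) | Yes | No, the reader must count |
| Adverse event tables by grade (SAP 5.8.2) | Only if recorded as an adverse event | Only those recorded |
| Indirect bilirubin and LDH change analysis (SAP 5.7.2.6) | Summary statistics and plots | No |
| Urine protein and microalbumin (SAP 5.8.3) | Related renal information | No |

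The one finer shift in the plan is serum ferritin by cut-points (SAP 5.7.2.3), which is an iron efficacy analysis.

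**Step 4. How many patients?** The documents do not give the share above range at entry. If it were 10%, 30% or 50% for a given test, then in the expansion cohort of 30 the number unable to show an upward shift would be 0.10 × 30 = 3, 0.30 × 30 = 9 or 0.50 × 30 = 15. These shares are assumptions that show the range and are not estimates.

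**Step 5. Which range?** SAP 5.8.3 refers to standard reference ranges. Protocol 11.2 assigns haematology (apart from nucleated red cells) and chemistry to each site's local laboratory, and the synopsis allows up to 15 centres. The SAP does not say whether the limit is the local one or a common one.

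**The case against.** The strongest reply is that nothing is hidden. SAP 5.2 requires minimum, median and maximum as well as mean and standard deviation, and 5.8.3 applies this to values and to changes by cohort and visit. In a dose escalation cohort of 5 or 6, an extreme creatinine would stand out. Every value is listed. Protocol 14.5 makes clinically relevant laboratory changes adverse events, and these are tabulated by patient and maximum grade. The Safety Review Team reviews chemistry results. The protocol promised shift tables only as appropriate, and the study is descriptive.

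Most of this stands, and it limits the point. A reader might infer that a severe symptomless rise would leave only a cohort mean and a listing, so that the renal risk could be reported as absent when it had occurred. The documents do not support that. The maximum is reported, the expansion cohort has 30 patients, urine protein and microalbumin are summarised, and a large rise would go unrecorded as an adverse event only if it caused no symptoms, did not stop treatment and was not thought clinically relevant. Nor do bilirubin and LDH depend on the shift table alone, since indirect bilirubin and LDH have their own change analysis.

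The reply does not supply the count. A maximum describes one extreme, not how many patients worsened, and the adverse event route depends on the investigator's assessment, so it is not an independent check on the laboratory data.

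**Conclusion.** The point holds for the shift tables and for the missing count. Under the stated rule, a patient above range at baseline cannot show an upward shift, and no planned laboratory table counts patients whose already abnormal value worsened. This follows from the wording of SAP 5.8.3 and the entry criteria and needs no assumption about the data.

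The practical size is unknown because the share of patients above range at baseline is not given. If few start above range, little is lost. This is a modest gap in safety reporting. It does not touch the primary endpoint and does not mean that a serious laboratory change would go unseen. It is worth correcting because creatinine is the marker tied to a risk that the protocol itself names, and the correction uses data already collected.

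**What to change.** In SAP 5.8.3:

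- Present the haematology and chemistry shifts by NCI-CTCAE v4.0 grade wherever a grade exists. The trial already uses this scale for adverse events.
- For creatinine, AST, ALT and total bilirubin, add the number of patients reaching stated multiples of ULN and stated multiples of their own baseline. Counting at any visit after the first dose would also catch a rise that settles before the end of treatment visit. The multiple of own baseline covers a large rise within the normal range.
- State that the ULN is that of each local laboratory, because Protocol 11.2 places these tests at the sites.

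The cost is SAP wording, standard programming and one or two more tables, with no new tests on patients. Protocol 15.2.3 leaves the form of the shift tables open, so its wording need not change. If the SAP is already signed off, SAP section 1 allows the departure to be described and justified in the study report. The change concerns reporting only and alters no dose or clinical rule.
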